## 11.2 Adverse Events

In addition to all SAEs, the following selected adverse events (AEs) are being collected as part of the RITAZAREM trial:

1. Infections (all episodes requiring treatment with intravenous (IV) or oral antibiotics or infections that are commonly understood to be opportunistic)
2. Occurrence of hypogammaglobulinemia (IgG <5g/l)
3. Occurrence of hypogammaglobulinemia (IgG <3g/l)
4. An adverse event that results in a change in dose of trial IMPs (rituximab, azathioprine, methotrexate or mycophenolate mofetil (MMF))
5. An adverse event that results in the addition of a relevant concomitant medication (see section 13.3.1 for list)
6. An adverse event manifested by the occurrence of a relevant laboratory abnormality (see section 13.3.2 for list)
7. New malignancies

Infections are recorded using the Infection Form and entered in the MACRO database. Frequency tables for serious and non-serious infections with date of onset occurring in the maintenance phase will be reported using the safety population and stratified by induction regime. The number of patients with newly occurring IgG < 5g/L and newly occurring IgG < 3g/L will be reported. Additionally, counts of subjects and events for non-serious infections will be reported, grouped by High Level Group Term and Preferred Term based on the MedDRA code.

Individual listings of infections are reported to the DSMB and reviewed quarterly.

New malignancies are recorded using the New Malignancy Form and entered in the MACRO database. All instances of new malignancies detected during the maintenance phase will be reported as individual listings sorted per patient by site. The following detail will be reported:

- Treatment arm
- Malignancy Detection date
- Malignancy Diagnosis date
- Malignancy Site
- Malignancy Type
- Malignancy Reoccurrence
- Malignancy Treatment (Surgery, Radiotherapy, Chemotherapy, Other)
- Malignancy Associated with SAE (Yes/No)
- Malignancy Comments

### 11.3 Hypogammaglobulinemia

Hypogammaglobulinemia is defined as a value of IgG < 5 g/L measured at any stage of the trial (including visits occurring during the induction period). Frequency tables for hypogammaglobulinemia will be reported using the full analysis population and stratified by treatment arm and:

- a) Induction regimen (1A/1B)
- b) ANCA type (anti-PR3/anti-MPO)
- c) Relapse type (Severe/Non severe)
- d) Previous treatment with rituximab (Yes/No)
- e) Previous treatment with cyclophosphamide (Yes/No)
- f) Previous treatment with rituximab or cyclophosphamide (Yes/No)
- g) Baseline (Screening/Month 0) IgG (g/L).

A logistic regression analysis will be carried out to predict hypogammaglobulinemia, using the above as predictor variables. Individual univariate models and a multivariate model will be considered. Outcomes (Estimate, 95% CI and P-value) will be surmised in tabular form.

These analysis are to be considered exploratory only, as they were not specified in the protocol and the data is observational.

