### **13.3 Expected Adverse Events/Serious Adverse Events (AE/SAE)**

All serious adverse events, including serious adverse drug reactions (see section 13.2) should be reported according to guidance in section 13.5.

In addition to all SAEs, the following selected adverse events (AEs) are being collected as part of the RITAZAREM trial.

1. Infections (all episodes requiring treatment with intravenous (IV) or oral antibiotics or infections that are commonly understood to be opportunistic)
2. Occurrence of hypogammaglobulinaemia (IgG <5g/l)
3. An adverse event that results in a change in dose of trial IMPs (rituximab, azathioprine, methotrexate or mycophenolate mofetil (MMF))
4. An adverse event that results in the addition of a relevant concomitant medication (see section 13.3.1 for list)
5. An adverse event manifested by the occurrence of a relevant laboratory abnormality (see section 13.3.2 for list)
6. New malignancies

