#### **13.3.1 Relevant concomitant medications**

1. Any anticoagulant, including warfarin, or newer equivalent agents, aspirin, clopidogrel, dipyridamole etc. This will identify any patient who has had a venous thromboembolic event or cardiovascular event – both important comorbidities in the AAV population.
2. IVIg – indicative of hypogammaglobulinaemia or recurrent infections
3. Any antibiotic, antiviral or antifungal agent – a corresponding infection form should have been completed, so this will act as an important cross check

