### 9.6.2 Concomitant Medication

Any relevant concomitant medication prescribed during the trial will be recorded in the Concomitant Medication Form at Screening, months 0 to 48 and Unscheduled visit if applicable. The data will be entered in the MACRO database and retained for safety monitoring. Data will be reported as table listings per patient, per study visit. The following information, when available, will be reported:

- Medication name (generic names only)
- Category (Anticoagulant/Antiplatelet, IVIg, Antimicrobial, Other)
- Dose (units)
- Frequency (one daily, twice daily, three times daily, four times a day, alternate days, weekly, other, as required)
- Comments

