## 11.6 Clinical Laboratory Evaluations

Clinical laboratory tests will be performed at baseline (either at Screening or Month 0, taking the latest value if assessment were performed at both visits), and at each visit in the maintenance phase (months 4, 8, 12, 16, 20, 24, 27, 30, 36, 42 and 48). Measured values will be recorded in the Clinical Laboratory Tests Forms and entered

in the MACRO database. Data management will ensure that any missing values are due to the test not being performed (“Not measured” tick-box).

The following variables will be summarised in accordance with section 9 using the full analysis population. Missing values will be assumed to be “not measured” without cross-referencing the relevant tick-box.

- Clinical Labs
  - Haemoglobin (g/dL)
  - Platelets (cells x 10^9/L)
  - WBC (cells x 10^9/L)
  - ESR (mm/h)
  - Creatinine (µmol/L)
  - CRP (mg/L)
  - ALT (U/L)
  - AST (U/L)
- ANCA
  - Anti-PR3 (positive/negative)
  - Anti-MPO (positive/negative)
  - ANCA status – derived variable, details in section 1.1
- Lymphocyte markers
  - CD19 (cells x 10^9/L and %)
- Immunoglobulins
  - IgG (g/L)
  - IgM (g/L)
  - IgA (g/L)

Table 8 lists the preferred unit for reporting and the multiplicative conversion factor (CF) employed for those clinical labs collected in the CRF using different measurement units.

---

 Conversion factors taken from <http://www.scymed.com/en/smnxfd/smnxfdac.htm>

Table 8: Conversion factors

Variable	Original unit	CF	Reporting unit
Haemoglobin	g/L	0.1	g/dL
Haemoglobin	mmol/L	1.611344	g/dL
WBC	cells x 10  /mm 	1	cells x 10  /L
Creatinine	g/dL	88.42 x 10 	µmol/L
Creatinine	mg/dL	88.42	µmol/L
CRP	mg/dL	10	mg/L
CD19	cells x 10  /mm 	1	cells x 10  /L
CD19	cells/µL	0.001	cells x 10  /L
IgG	mg/dL	0.01	g/L
IgM	mg/dL	0.01	g/L
IgA	mg/dL	0.01	g/L

Laboratory values outside the ranges detailed in Table 8 will be considered un-physiological, and will be considered outliers and excluded from the analysis. All such values will be listed in a separate table (grouped by item, subject, and visit) and queried by the data manager.

Table 9: Physiological ranges for laboratory tests

Variable	Minimum	Maximum	Reporting unit
Haemoglobin	5	20	g/dL
Platelets	5	900	cells x 10  /L
WBC	1	40	cells x 10  /L
ESR	0	200	mm/h
Creatinine	30	1500	µmol/L
CRP	0	600	mg/L

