Figure 29: Forest plot of cox proportional hazards model – Tertiary endpoint.

Figure 30: Serious Adverse Events, forest plot of frequency and relative risk by treatment arm.

Figure 31: Non–serious infections, forest plot of frequency and relative risk by treatment arm.

Figure 32: Kaplan–Meier plot of SAE–free survival by treatment arm.

Figure 33–45: Boxplots by treatment arm of continuous clinical lab tests:  
Haemoglobin, Platelets, WBC, ESR, Creatinine, CRP, ALT, AST, CD19, CD19 (%), IgG, IgM, and IgA.

Figure 46–48: Stacked bar charts by treatment arm of discrete clinical lab tests:  
Anti–PR3, Anti–MPO, and ANCA status.

Figure 49: Alluvial plot of ANCA status by treatment arm, showing change from month 4 to month 24 and to month 36.

Figure 50: Bar charts of EQ–5D–5L questionnaire item's responses.

Figure 51: Boxplot of EQ–5D–5L index totals (VAS Health state, OTT utility score, and VAS utility score) by treatment arm.

Figure 52–54: Bar charts of PROMIS questionnaire item's responses (fatigue, pain, physical ability).

Figure 55: Bar chart of PROMIS questionnaire sub–totals by treatment arm.

Figure 56: Boxplots of PROMIS questionnaire sub–totals by treatment arm.

Figure 57: Boxplot of PROMIS questionnaire total score by treatment arm.

Figure 58–63: Bar charts of SF–36 questionnaire item's responses.

Figure 64: Boxplot of SF–36 questionnaire sub–totals by treatment arm.

Figure 65: Boxplot of SF-36 questionnaire PCS and MCS components by treatment arm.

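### The IgG safety outputs take no account of IVIg replacement: visit summaries mix native and replaced IgG, and the < 3 g/L count can miss patients

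*SAP*

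**What the plan says.** **How low IgG is counted.** SAP 11.3 sets the definition: "Hypogammaglobulinemia is defined as a value of IgG < 5 g/L measured at any stage of the trial". Induction visits are included, and the logistic models of section 11.3 are labelled exploratory. SAP 11.2 adds: "The number of patients with newly occurring IgG < 5g/L and newly occurring IgG < 3g/L will be reported".

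**How IgG is summarised.** IgG in g/L is one of the laboratory variables in SAP 11.6, which says: "The following variables will be summarised in accordance with section 9 using the full analysis population". Under SAP 9 that means n, mean, standard deviation, median, minimum and maximum, by arm. SAP 13 adds figures, IgG among them: "Boxplots by treatment arm of continuous clinical lab tests".

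**What is done with IVIg.** Protocol 13.3.1 lists it as a relevant concomitant medication and gives the reason: "IVIg – indicative of hypogammaglobulinaemia or recurrent infections". Under Protocol 13.3, an adverse event that leads to its addition is a selected adverse event. Protocol 13.4 has the indication for a new concomitant medication recorded on the adverse event page. SAP 9.6.2 makes IVIg a named category, but of the concomitant medication output it says: "Data will be reported as table listings per patient, per study visit". No table of IVIg by arm is specified. SAP 11.2, 11.3, 11.6 and 13 do not mention IVIg.

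**The concern.** IgG measured after IVIg is partly donor IgG, so it no longer shows what the patient's own immunoglobulin level is doing. Protocol 10.2 excludes IVIg in the three months before entry. Entry values are therefore largely native, while follow-up values may not be, and a comparison over time mixes the two.

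Long-term rituximab safety is a secondary objective. Protocol 7.3.1 reports that repeat dosing in the pilot cohort caused no significant fall in immunoglobulin levels. The visit-wise IgG outputs are where a reader will look to see whether that holds here, and replacement can imitate the reassuring answer. The 11.3 event includes induction visits, when every patient receives rituximab. Evidence specific to the maintenance comparison therefore rests largely on the newly occurring counts and the visit summaries.

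**Working it through.** The plan states no figure to reproduce. The check has two parts: how each planned output behaves once IVIg is given, and an illustration of size.

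**1. Behaviour of each output.** Three made-up patients, IgG in g/L at successive visits:

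| Patient | IgG values | IVIg starts after | Ever < 5 (11.3) | < 3 seen (11.2) | Last value in 11.6 |
|---|---|---|---|---|---|
| A | 8, 6, 4.5, 7, 7.5 | 4.5 | yes | no | 7.5 |
| B | 8, 6, 5.5, 7, 7.5 | 5.5 | no | no | 7.5 |
| C (assumed to reach 2.8 without IVIg) | 8, 6, 4.5, 6, 6 | 4.5 | yes | no | 6 |

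- A stays counted in 11.3. The later rise hides nothing in that endpoint.
- B is lost from the < 5 counts if IgG would otherwise have fallen below 5.
- C is counted for < 5 but missed for < 3.
- All three raise the late-visit summaries and boxplots.

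**2. Size.** Input from the documents: at least 160 randomised 1:1 (Protocol 16.3 and 9.1), so about 160 / 2 = 80 per arm. Inputs assumed, because the documents give none of them:

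- f, the share of an arm on IVIg (at the visit for the mean, at any time for the count): 2% to 10%
- r, the rise in measured IgG on IVIg: 2 to 4 g/L
- s, the share of IVIg users who start before any recorded IgG < 5: 0 to 100%

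Shift in the arm mean at a visit = f × r:

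| f | r = 2 g/L | r = 4 g/L |
|---|---|---|
| 2% | 0.04 | 0.08 |
| 5% | 0.10 | 0.20 |
| 10% | 0.20 | 0.40 |

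Most patients that can be lost from the ever-< 5 count = 80 × f × s:

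| f | s = 0 | s = 25% | s = 50% | s = 100% |
|---|---|---|---|---|
| 2% | 0 | 0.4 | 0.8 | 1.6 |
| 5% | 0 | 1.0 | 2.0 | 4.0 |
| 10% | 0 | 2.0 | 4.0 | 8.0 |

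For s of 25% or more, that is 0.4 / 80 = 0.5 to 8 / 80 = 10 percentage points. It is an upper limit, because some patients who start IVIg early would never have fallen below 5. If every IVIg user already had a recorded low value, the loss is zero at any f.

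**The case against.** The strongest objection is that section 11.3 is an ever-event. A reader might infer that treated patients look recovered and so drop out of the hypogammaglobulinaemia endpoint. They do not: one recorded value below 5 g/L counts permanently. Immunoglobulins are also scheduled at every visit from month 0 to month 48, which limits how often IVIg would precede a recorded low value. This stands. Some room remains, because visits after month 4 are three to six months apart and IVIg may be started for recurrent infection.

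Other stronger readings also lack support:

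- **That the distortion falls mainly on the rituximab arm.** No IVIg rate by arm and no rule for starting it is given. Both arms receive rituximab induction, and control patients may receive mycophenolate, for which Protocol 11.4 reports hypogammaglobulinaemia.
- **That a patient replaced below 5 g/L can never be seen below 3 g/L.** Replacement makes this less likely, but nothing in the documents rules it out.
- **That the share below 5 g/L at a given visit would be understated.** The SAP plans no such by-visit proportion. IgG is summarised there as a continuous variable.

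IVIg is also not wholly ignored. It appears in the 9.6.2 listings, and IgG < 5 g/L is flagged at data entry and reported to the DSMB every six months (Protocol 13.4.2). But the listing is not linked to IgG, and the flag again rests on measured values.

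Finally, hypogammaglobulinaemia is not a primary or secondary endpoint, the mean shift is small over the assumed range, and a median would usually move less. These points limit the importance of the gap but do not close it.

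**Conclusion.** The concern holds in a limited form. No planned IgG analysis takes account of IVIg.

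- **Visit summaries and boxplots (11.6, 13):** affected whenever anyone is on IVIg. The assumed ranges raise an arm mean by about 0.04 to 0.4 g/L.
- **Newly occurring < 3 g/L (11.2):** can miss patients who start IVIg at 3 to 5 g/L. The documents do not allow the number to be set.
- **< 5 g/L counts (11.2, 11.3):** understated only where IVIg precedes any recorded value below 5. The loss runs from zero to at most 8 of 80 patients over the assumed ranges.

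These sizes rest on assumed IVIg use and IgG rise, and neither the true size nor the direction between arms can be derived from the documents. The outputs concerned are safety outputs, with the 11.3 models exploratory. The primary analysis is unaffected.

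**What to change.** Analysis rules only; nothing here bears on when IVIg is given.

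1. **SAP 11.2 or 9.6.2:** tabulate IVIg starts after randomisation by arm and recorded indication.
2. **SAP 11.2 and 11.3:** keep the measured-only < 5 and < 3 g/L counts. Beside the newly occurring < 5 g/L count, read as post-randomisation, add a supplementary row for *IgG < 5 g/L or IVIg start*. Use the same period for both components, and show separately the IVIg starts whose recorded indication is not low IgG.
3. **SAP 11.6 and the boxplots:** give the number on IVIg at each visit by arm and report post-IVIg IgG values separately. State that simply dropping those values also removes the most affected patients, so an exclusion alone would not be neutral.

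The cost is SAP wording, one table, one extra row, and a merge of the concomitant medication and laboratory data. IVIg is already a coded category and its indication is captured, so no new data are needed. SAP 9.6.2 does not list a start date among the reported items. If none is held, the first visit at which IVIg is recorded can stand in for it. The downside is that some IVIg may be given for reasons other than low IgG, so the combined row will include patients whose IgG was never low. That is why both counts are shown and the indication is split out.

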## 9.1 Subject Disposition

### 9.1.1 Visit dates

The three phases of the trial are defined as follows:

1. Induction phase: enrolment to Month 4 (inclusive)
2. Maintenance phase: Month 4 to Month 24 (inclusive)
3. Follow-up phase: Month 24 (exclusive) to Month 36/42/48 (common close)

A target randomisation date (*RandomDate*) four months in the future was generated at enrolment to help local sites organise rituximab or azathioprine supply for the maintenance phase. Patients could be randomised from 14 days before to 14 days after Month 4 visit. If patients attended their Month 3 visit and were in remission, then they could be randomised up to 14 days before Month 4. Those not in remission at Month 3 were reassessed at Month 4 and, if they entered remission, were then randomised and commenced allocated therapy within the next 14 days. Those not in remission at Month 4 were not randomised (even if they had been considered in remission at Month 3 visit) and treated at the investigator's discretion, follow-up data continued to be collected unless consent was withdrawn. **Maintenance therapy (with either treatment) was not administered before the Month 4 visit.** Consequently, the month 4 visit will be considered as both the end of the Induction Phase of the trial and the beginning of the Maintenance Phase of the trial. It will be used as time zero for the primary endpoint of the Maintenance Phase (time to disease relapse from randomisation).

When calculating time elapsed in days, months or years (e.g. when calculating time from randomisation), full dates (yyyy-mm-dd) appropriately formatted, will be converted to the number of days since 1970-01-01, with negative values for earlier dates, following the default representation of dates in the R language. A full year is taken to be 365.25 days long, a standardisation that approximates for the

---

 <https://stat.ethz.ch/R-manual/R-devel/library/base/html/Dates.html>

occurrence of leap years. A month is taken to be 1 / 12th of a full year. First day of the month/year will be used for fuzzy dates.

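### SAP 11.3 tabulates hypogammaglobulinaemia by randomised arm but counts cases from before the month 4 visit, which dilutes the arm comparison if any such cases exist

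*SAP*

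**What the plan says.** SAP 11.3 defines a case as IgG below 5 g/L "measured at any stage of the trial (including visits occurring during the induction period". It then states: "Frequency tables for hypogammaglobulinemia will be reported using the full analysis population and stratified by treatment arm and" a list of seven factors, a) to g). The last of these is "Baseline (Screening/Month 0) IgG (g/L"). On modelling it says: "A logistic regression analysis will be carried out to predict hypogammaglobulinemia, using the above as predictor variables", with univariate and multivariate versions. The section closes with a limit on its use: "These analysis are to be considered exploratory only, as they were not specified in the protocol and the data is observational".

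SAP 9.1.1 fixes the phases. The first is "Induction phase: enrolment to Month 4 (inclusive"), and maintenance therapy was not given before the month 4 visit in either arm. Month 4 is therefore the end of induction, the start of maintenance and time zero for the primary endpoint.

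Two other safety sections bear on the point. SAP 11.1 has separate tables for serious adverse events with onset after randomisation and leaves induction events to the induction-phase report. SAP 11.2 promises a count of new cases: "The number of patients with newly occurring IgG < 5g/L and newly occurring IgG < 3g/L will be reported". It does not say which visit new is judged against or over what period.

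**The concern.** The schedule of events places immunoglobulin measurements at months 0, 1.5, 3 and 4, and then at every later visit. Up to four measurements that can make a patient a case therefore come before or at time zero. All patients receive rituximab in induction, earlier rituximab or cyclophosphamide is allowed at entry, and no exclusion criterion sets a minimum IgG. Some patients could plausibly be below 5 g/L by month 4, although the documents do not say how many.

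Randomisation shares such patients equally between the arms in expectation. They add the same amount to both rates and tell the reader nothing about maintenance rituximab against azathioprine. Long-term safety of rituximab is a secondary objective, and the protocol's rationale cites pilot data without a significant fall in immunoglobulins. A table that leans towards no difference could seem to confirm that finding.

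A second, separate problem concerns the predictor list. Month 0 IgG is offered as an explanation for an outcome that month 0 IgG can itself trigger.

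**Working it through.** The plan gives no figure for this analysis, so there is none to reproduce. The rates below are assumptions chosen to show direction and scale.

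**1. Dilution of the by-arm tables**

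Let q be the share of randomised patients with IgG below 5 g/L by the month 4 visit, taken as equal in the two arms. Let p be the risk of a new case after month 4 among the rest. The any-stage rate in an arm is q + (1 − q)p, so the risk difference between arms is (1 − q) times the difference in new-case risk.

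Assume p = 0.10 for azathioprine and 0.20 for rituximab. The true risk ratio is 2.0 and the true odds ratio is (0.20/0.80)/(0.10/0.90) = 2.25.

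| q | Azathioprine, any stage | Rituximab, any stage | Risk ratio | Risk difference |
|---|---|---|---|---|
| 0 | 0.100 | 0.200 | 2.00 | 0.100 |
| 0.05 | 0.05 + 0.95 × 0.10 = 0.145 | 0.05 + 0.95 × 0.20 = 0.240 | 1.66 | 0.095 |
| 0.10 | 0.10 + 0.90 × 0.10 = 0.190 | 0.10 + 0.90 × 0.20 = 0.280 | 1.47 | 0.090 |
| 0.20 | 0.20 + 0.80 × 0.10 = 0.280 | 0.20 + 0.80 × 0.20 = 0.360 | 1.29 | 0.080 |

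With assumed new-case risks of 10% and 25%, the risk ratio of 2.50 falls to 1.98, 1.71 and 1.43 at the same three non-zero values of q. At q = 0 there is no dilution under either assumption. The direction does not depend on the rates chosen; only the size does.

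**2. Whether the logistic model is affected**

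The model takes its predictors from the list above it. Items a) to g) are induction regimen, ANCA type, relapse type, prior rituximab, prior cyclophosphamide, either of these two, and baseline IgG. Treatment arm appears in the sentence that introduces the list but is not an item in it. If arm is left out, the model estimates no arm effect and there is nothing to dilute.

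If arm is included, a univariate model at q = 0.20 would show an odds ratio of (0.36/0.64)/(0.28/0.72) = 1.45 in place of 2.25. In a simulation of that case, adjusting for baseline IgG brought the odds ratio back to about 1.7 when all the early cases were low at month 0. It made almost no difference (about 1.45) when they all arose during induction.

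**3. Baseline IgG as predictor and as part of the outcome**

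A patient with month 0 IgG below 5 g/L is a case whatever happens later. To isolate the effect of this overlap, 2,000 trials of 160 patients were simulated. Baseline IgG was normal with SD 2.5 g/L, and 20% of patients had a low value after randomisation, independently of baseline. A logistic model on baseline IgG then gave:

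| Patients with baseline below 5 g/L | Odds ratio per g/L, any-stage outcome | Share of runs with p < 0.05 | Same share, post-randomisation outcome |
|---|---|---|---|
| 2% | 0.90 | 27% | 6% |
| 5% | 0.82 | 70% | 4% |
| 11% | 0.70 | 99% | 4% |

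The post-randomisation outcome gave an odds ratio of about 1.00 in all three settings. The overlap can therefore create an association where none exists. In practice low baseline IgG probably does predict later low IgG, so the overlap would add to a real association.

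**The case against.** The strongest reply is that little rests on this section. It is labelled exploratory, hypogammaglobulinaemia is a selected adverse event and not a listed endpoint, and the stated aim of the model is prediction. IgG after randomisation can also be seen elsewhere. SAP 11.6 summarises it at every visit from month 4 to month 48, section 9 gives summary tables a column per arm, section 13 lists IgG boxplots by arm, and 11.2 adds the count of new cases. All of this stands and limits the severity. It does not repair the 11.3 tables, and the 11.2 count has no reference visit or window.

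A reader might infer more than the documents support:

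- **That the plan's only model of hypogammaglobulinaemia is biased against finding an arm effect.** Arm is not in list a) to g), so what can be shown is an ambiguity.
- **That the model is circular.** The overlap acts only through patients whose baseline IgG is already below 5 g/L. For everyone else baseline IgG is an ordinary predictor.
- **That this is the trial's main safety signal.** No document ranks it so. The listed safety endpoints are severe adverse events and infections.

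A further objection concerns the remedy. Induction regimen and prior rituximab or cyclophosphamide can lower IgG before month 4. Moving the whole risk-factor model to after month 4 and adjusting for month 4 IgG would condition on an intermediate and could hide those effects. This is correct, and the fix below is limited accordingly.

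**Conclusion.** The by-arm tables in SAP 11.3 mix values from before and after time zero, and any case already present by month 4 dilutes the arm contrast. The risk difference shrinks by the factor 1 − q. Under assumed new-case risks of 10% and 20%, a risk ratio of 2.0 reads as 1.66 to 1.29 for q between 5% and 20%, and stays at 2.0 if q is zero. The documents give neither q nor the new-case risks, so the direction is firm and the size is not.

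For the logistic model, the dilution is conditional on arm being included, and the SAP does not settle this. The inflation of the baseline-IgG association is real but partial.

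The point is worth correcting because SAP 11.1 already separates events at randomisation and 11.3 departs from that practice. It does not touch the primary analysis, and it does not show that an effect of rituximab on IgG would be hidden.

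**What to change.** 1. **By-arm tables, and any model used to estimate an arm effect.** Count the first IgG below 5 g/L after the month 4 visit among patients at or above 5 g/L at month 4. Use month 4 IgG as a covariate in that arm model. List induction-phase cases separately, as 11.1 does for serious adverse events.
2. **Risk-factor model.** Keep the any-stage version as exploratory. Whenever baseline IgG is a predictor, count only cases arising after baseline in patients at or above 5 g/L at baseline. Do not add month 4 IgG to this model.
3. **Clarifications.** State whether treatment arm is a predictor in the logistic model. In 11.2, give the reference visit and time window for newly occurring cases. Because laboratory results may fall up to two weeks either side of a visit, say by date which sample counts as the month 4 value, and what is done if it is missing.

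The cost is SAP wording and a small change to derived variables, since IgG is already scheduled at month 0, month 4 and every later visit. Patients already low leave the relevant denominator and appear in the separate listing. With about 80 patients per arm and q = 10%, that leaves about 80 × 0.90 = 72 per arm for the arm comparison.
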